7.1.2.3. Hypothesis: Albuterol Use Will Increase Several Days Prior to a CE-COPD

The hypothesis under consideration is that albuterol use will increase several days prior to a CE-COPD. Several days will be defined as 7 days prior to the date of the CE-COPD symptom peak for this analysis.

For each subject that experiences at least 1 CE-COPD, Y_1, \dots, Y_7 will represent the number of puffs of albuterol during the 7 days preceding the date of the CE-COPD symptom peak and Y_8, \dots, Y_{14} will represent the number of puffs taken each day during days 8 through 14 preceding the date of the CE-COPD symptom peak. Under the hypothesis of no increased albuterol use

preceding an exacerbation (ie, null hypothesis) assume for subject "xxx" that $Y_i \stackrel{iid}{\sim} \text{Poisson}(\lambda_{xxx})$ for all subjects i. Alternatively, if albuterol use does increase prior to an exacerbation, then

$Y_i \stackrel{iid}{\sim} \text{Poisson}(\lambda_{xxx})$ during day 8 through 14 preceding the date of the CE-COPD symptom peak

and $Y_i \stackrel{iid}{\sim} \text{Poisson}(\lambda_{xxx} + \delta)$ for the immediate 7 days preceding the CE-COPD(s). Also, for random subject effect, assume λ_{xxx} follows some distribution to account for subject to subject variability. Let d_{xxx} will equal to the mean number of puffs during the 7 days immediately preceding the date of the CE-COPD symptom peak minus mean number of puffs during days 8 through 14 preceding the date of the CE-COPD symptom peak. To assess if albuterol usage increases 7 days prior to a CE-COPD, $H_0: \mu_D = 0$, $H_1: \mu_D > 0$ will be tested using a t-test at the 0.05 significance level.

7.1.2.4. Number of Days Prior to the Peak of a CE-COPD When Albuterol Use Increased

Among patients who experienced a CE-COPD, summary statistics of the number of days prior to the peak of a CE-COPD when albuterol use increased, will be presented overall and by moderate CE-COPDs and severe CE-COPDs for 3 thresholds defining an increase in albuterol use;

- (i) First occurrence of a single day increase of 20% from baseline use prior to CE-COPD
- (ii) First occurrence of a single day absolute increase of 2 inhalations from baseline use prior to CE-COPD
- (iii) First occurrence of a single day absolute increase of 4 inhalations from baseline use prior to CE-COPD

Among patients who did not experience a CE-COPD, summary statistics, including 95% CIs intervals of the proportion of eMDPI time on study days when a patient exceeded a given threshold of albuterol use (number of days a given patient's single day's albuterol use exceeded 4 inhalations/total number of eMDPI study days for a given patient), will be summarized for 3 thresholds defining an increase in albuterol use;

- (i) First occurrence of a single day increase of 20% from baseline use
- (ii) First occurrence of a single day absolute increase of 2 inhalations from baseline use
- (iii) First occurrence of a single day absolute increase of 4 inhalations from baseline use

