c. Final Visit/Early Termination Visit (Visit 5, Day 84 ±14 days)

The following procedures and assessments will be performed at visit 5 or Early Termination Visit:

- physical examination, including height and weight
- urine pregnancy test for women of childbearing potential
- assess for COPD exacerbations
- inquire about adverse events
- collect wearable accelerometer, if applicable.
- collect ABS eMDPI
- concomitant medication inquiry

3. Exacerbation Visit (Vz [Up to 14 days after CE-COPD start date])

In the case of a CE-COPD (defined in Section 6.1.1 of the protocol), the patient will be required to return to the investigational center. The exacerbation visit should be conducted up to 14 days after the CE-COPD start date. The date and reason for the unscheduled visit will be recorded on the electronic case report form as well as any other data obtained from procedures and assessments.

Procedures performed during exacerbation visit include the following:

- physical examination, including weight
- inquire about adverse events
- concomitant medication inquiry
- collect all ABS eMDPI devices used prior to CE-COPD and dispense additional ABS eMDPI if needed

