1. STUDY OBJECTIVES AND ENDPOINTS

1.1. Objectives and Endpoints

The objectives of this study are to explore the pattern and amount of albuterol use (as captured in the albuterol sulfate (ABS) multidose dry powder inhaler with an eModule (eMDPI), alone or in combination with other study data, preceding a moderate or severe CE-COPD (as diagnosed by the investigators per the protocol). The hypothesis is that albuterol use will increase several days prior to a moderate or severe CE-COPD and can serve as a marker of COPD deterioration.

The endpoints of the trial are the primary outcome measure (ie, CE-COPD) and the primary outcome predictor (ie, albuterol use) alone or in combination with secondary predictors (ie, other study data). These predictors of CE-COPD will be modeled to determine which patterns best predict the subsequent development of CE-COPD.

For albuterol use, parameters of interest will include (1) the total number of inhalations in the days preceding the peak of a CE-COPD, (2) the number of days prior to the peak of a CE-COPD when albuterol use increased, and (3) the number of albuterol uses in the 24 hours preceding a CE-COPD. Therefore, endpoints are not designated as either primary or secondary.

In addition to albuterol use, inspiratory flow values (maximal inhalational flow (MIF), inhalational volume, inhalation duration, and time to MIF), sleep disruption index (SDI), total daily steps (TDS), and baseline information regarding disease state and demographics will be studied. These data will be analyzed using both a univariate and multivariate approach, to determine which patterns best predict the subsequent development of a CE-COPD. Inspiratory flow values are obtained from the eMDPI, SDI is obtained for a subset of patients who agree to participate at specific investigational centers (n=100) from an accelerometer worn on the wrist, and TDS is obtained for a subset of patients who agree to participate at specific investigational centers (n=100) from an accelerometer worn on the ankle. Baseline disease state and demographic information will be obtained at screening.

Another objective for this study is to evaluate the safety of ABS eMDPI use in patients with exacerbation-prone COPD.

The safety endpoints for this study include the following:

- adverse event data
- physical examinations

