7.1.2. Analysis Methods for Albuterol Use

7.1.2.1. Pattern of Baseline Daily and Weekly Albuterol Use

A patient's pattern of baseline albuterol use is exhibited if, on any given day, during a given week, they do not take more than their average number of inhalations computed from day 1 to day 7.

Summary statistics including 95% CIs intervals of the proportion of patients exhibiting their individual weekly baseline albuterol use during each week of the 12 week study (Week 1, Week 2,..., Week 12) will be presented overall and by CE-COPD status and by CE-COPD severity (Yes: severe, moderate; No).

Summary statistics including 95% CIs intervals of the proportion of eMDPI time on study days when a patient did not take more than the average number of inhalations computed from day 1 to day 7 (number of days a given patient had no more than average baseline albuterol use) / total number of eMDPI study days for a given patient) will be summarized overall and by CE-COPD status and by CE-COPD severity (Yes: severe, moderate; No).

Week 1 and Week 2 and the first 14 day patient albuterol use patterns, "WK1:I#iD#dMTN#n," "WK2:I#iD#dMTN#n" and "D14:I#iD#dMTN#n" designation, will be summarized descriptively (counts and percent) overall and by CE-COPD status and by CE-COPD severity (Yes: severe, moderate; No).

7.1.2.2. Total Number of Inhalations in the Days Preceding the Peak of a CE-COPD

For patients who experienced a CE-COPD, summary descriptive statistics of the total number of inhalations taken in 1 day (eg, the 24-hour period on the day prior to the date of the CE-COPD symptom peak) and at 3, 5, 7, 10, 14, and 21 days preceding the date of the CE-COPD symptom peak, will be presented overall and by moderate CE-COPDs and severe CE-COPDs.

In this analysis, among patients experiencing more than 1 CE-COPD, the subsequent CE-COPDs can be considered a separate CE-COPD, distinct from the first (preceding) CE-COPD, provided the patient exhibited at least 1 day of baseline albuterol use after the first (preceding) CE-COPD's end date, as captured on the adverse event page, and prior to the subsequent CE-COPD's start date, as captured on the adverse event page. For patients who experience multiple CE-COPDs, all distinct CE-COPDs will be considered in this descriptive analysis. Descriptive summaries of the number of inhalations on the days prior to a CE-COPD will only be reported if the event does not overlap with a preceding CE-COPD. For example, if the date of symptom

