7.5.2.1. Within Patient CE-COPD Analyses

For each CE-COPD event occurring at least 2 weeks after baseline, device-use measures (albuterol use, inhalational flow [MIF], inhalational volume, and time to MIF) will be summarized for each of 2 weeks of interest: first- 'CE-COPD-adjacent week', the week immediately preceding the onset of CE-COPD symptom (ie, day 1 through 7 preceding the date of the CE-COPD symptom onset), and second – 'CE-COPD-Prior Adjacent week', the week preceding that week (ie, during day 8 through 14 preceding the date of the CE-COPD symptom onset). Summary measures of daily and or weekly use will be compared between the two weeks, as proposed below:

Albuterol use measures:

- total number of inhalations in that week
- the maximal daily number of inhalations in that week
- the mean number of daily inhalations (ie, total number of inhalations divided by number of days with number>0)
- occurrence of a single day's albuterol use exceeding 4 inhalations
- occurrence of a single day's albuterol use exceeding 8 inhalations
- occurrence of a single day's albuterol use exceeding 12 inhalations
- number of days when albuterol use exceeding 4 inhalations
- number of days when albuterol use exceeding 8 inhalations
- number of days when albuterol use exceeding 12 inhalations

To note, in this analysis, no inhalation in any day will be taken as a 0 count.

Inhalation flow values parameters:

- maximal daily MIF during the week
- minimal daily time to MIF within a week
- maximal total daily inhalational volume within a week

To note, if no inhalation was taken at a specific day, flow value parameters will be missing and will not be imputed.

Analysis will be based on all patients CE-COPDs for which there are 14 days (or more) prior to the CE-COPD onset, where patient has been on study and CE-COPD free.

Descriptive statistics of use measures in the 'CE-COPD-adjacent week' and 'CE-COPD-Prior Adjacent week' will be presented.

Continuous measures will be compared between the 2 weeks using paired t-test (and Wilcoxon Signed Ranks test) whereas binary patterns will be compared using Mc-Nemar test.

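### The hypothesis test in SAP 7.1.2.3 counts both weeks back from the symptom peak, so a rejection does not show that albuterol use rose before the exacerbation began

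*SAP*

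**What the plan says.** SAP 1.1 states the aim: "albuterol use will increase several days prior to a moderate or severe CE-COPD and can serve as a marker of COPD deterioration". SAP 7.1.2.3 is the section headed as the test of that hypothesis. It fixes the window: "Several days will be defined as 7 days prior to the date of the CE-COPD symptom peak for this analysis". The tested quantity is the patient's mean daily puffs over days 1-7 before the peak minus the mean over days 8-14 before the peak. The null of zero is tested against a positive mean difference by t-test at 0.05. In the same section the alternative model places the raised rate in the week before the CE-COPD itself, and the conclusion is worded as a rise before a CE-COPD.

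SAP 7.5.2.1 compares the same pair of weeks from a different anchor, the first being "day 1 through 7 preceding the date of the CE-COPD symptom onset". It also restricts the events: "Analysis will be based on all patients CE-COPDs for which there are 14 days (or more) prior to the CE-COPD onset", with the patient on study and free of CE-COPD throughout. Section 7.1.2.3 has no such restriction. SAP 7.5.2 introduces this comparison as one of several correlation analyses, and no alpha or sidedness is given for it.

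The SAP treats start, peak and end of an event as separate dates. SAP 7.1.2.2, for example, uses the "start date, as captured on the adverse event page" alongside the date of symptom peak.

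**The concern.** A marker of deterioration is useful if it moves before the exacerbation. By definition a CE-COPD involves at least 2 consecutive days of worsening symptoms (SAP 7.5.1), so the peak can fall after onset. Each day between the two then counts in the week labelled as preceding the event. Patients may well use more rescue inhaler on those days, which makes the difference positive even if use was flat until symptoms began.

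A rejection would be valid evidence that use rises before the peak. It would not be evidence for the hypothesis as worded. The onset version could give a different answer, and the SAP does not say which of the two the report should rely on. No sensitivity analysis is planned (SAP 8).

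**Working it through.** **1. The plan's event count.** From SAP 2.3: 360 evaluable patients, 1.05 and 1.14 events per year (midpoint 1.095), 12 weeks.

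- Expected events: 360 × 1.095 × 12/52 = 91.0. The plan says 91.
- Poisson 95% limits for a mean of 91: 73 to 110. The plan gives the same range.
- P(at least 70 events) for a mean of 91: 0.990, in line with the plan's figure.

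**2. Patients contributing to the test.** The plan states no power or sample size for 7.1.2.3. With Poisson events, patients with at least one event = N × [1 − exp(−rate × 12/52)].

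- Central: 360 × [1 − exp(−1.095 × 12/52)] = 80.4.
- Range: 360 at 1.05/year gives 77.5; 400 at 1.14/year gives 92.5.

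I use n = 80.

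**3. Expected difference when nothing changes before onset.** Let the gap be the days from onset to peak, and let use rise only from onset. For a gap of up to 7 days:

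expected difference = gap × proportional rise × baseline use / 7

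The documents give no gap, rise, baseline use or day-to-day variability, so all four are assumed. At 4 inhalations/day:

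- 1-day gap, +25%: 1 × 0.25 × 4 / 7 = 0.14 per day
- 3-day gap, +50%: 3 × 0.50 × 4 / 7 = 0.86 per day

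For a gap of 7 to 14 days, the onset-to-peak days also fill the reference week. With a rise of δ per day the difference becomes δ × (14 − gap)/7, reaching zero at 14 days. There the test would miss a real increase. Counted from a correct onset date, the expected difference is zero at any gap.

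**4. How often the 7.1.2.3 test rejects.** Simulation with 6,000 trials per scenario: one event per patient, gamma between-patient rates (CV 0.5, assumed), gamma-Poisson daily counts, one-sided t-test at 0.05, n = 80, 4 inhalations/day, no change before onset. Overdispersion 0 is the SAP's own Poisson model.

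| Gap | Rise | Poisson | Overdispersion 0.25 | Overdispersion 1.0 |
|---|---|---|---|---|
| 1 day | +25% | 0.317 | 0.200 | 0.118 |
| 1 day | +50% | 0.751 | 0.454 | 0.236 |
| 2 days | +25% | 0.747 | 0.459 | 0.236 |
| 2 days | +50% | 0.998 | 0.914 | 0.564 |
| 3 days | +25% | 0.963 | 0.734 | 0.396 |
| 3 days | +50% | 1.000 | 0.997 | 0.837 |

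With no gap at overdispersion 0.25 the rate is 0.044 to 0.050, and with an exact onset anchor 0.049 to 0.050.

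Other inputs at overdispersion 0.25, each from (1 day, +25%) to (3 days, +50%):

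- 2 inhalations/day: 0.159 to 0.976
- 6 inhalations/day: 0.219 to 0.999
- n = 60 at 4/day: 0.166 to 0.984

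**5. Onset dated late.** At overdispersion 0.25, the onset-anchored test rejects in 0.194 (+25%) or 0.458 (+50%) of trials if onset is recorded 1 day late, and in 0.451 or 0.907 if 2 days late.

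**The case against.** The peak anchor is stated openly and has a basis. Two of the protocol's three albuterol parameters count from the peak, and SAP 7.5.1 measures time to CE-COPD to the date of symptom peak. A moderate or severe event also needs steroids and/or antibiotics plus an encounter or hospitalization, so days of early symptoms may precede the point at which it qualifies. The study is exploratory, its endpoints are unranked, and 7.5.2.1 will put an onset result beside the peak result. Onset dates may also be poor: "The exacerbation visit should be conducted up to 14 days after the CE-COPD start date", so the date may be recorded after the fact, and an onset dated 1 day late performs much like the peak anchor with a 1-day gap.

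Part of this stands. The peak comparison is a legitimate description, the rejection rates are illustrative, and the gain from an onset anchor shrinks as dating worsens. It does not remove the problem. The peak-based parameters are not the hypothesis, which is worded as a rise before a CE-COPD, and the SAP keeps onset and peak as separate dates. For gaps of up to 7 days, an onset dated no later than the peak cannot let in more post-onset days than the peak anchor does. Planning both analyses without saying which decides leaves the formally specified test, anchored on the peak, to be read as the answer.

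**Conclusion.** The concern holds. The test in 7.1.2.3 addresses a rise before the symptom peak, while its hypothesis and conclusion refer to a rise before the CE-COPD. With use flat until onset and 4 inhalations/day, gaps of 1 to 3 days and rises of 25% to 50% give rejection in 20% to over 99% of trials at overdispersion 0.25, 32% to about 100% under Poisson, and 12% to 84% at overdispersion 1.0. These are not type I error rates for a null about the peak. They show how often the result could be misread as early warning. If onset and peak share a date, the two tests coincide and nothing is lost. Because the study is exploratory and the onset comparison is already planned, this is a correction that should be made, not one that undermines the study.

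**What to change.** Choose one of two changes to the SAP:

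- In 7.1.2.3, count days 1-7 and 8-14 back from the symptom onset date used in 7.5.2.1, and apply that section's 14-day CE-COPD-free requirement.
- Or state that the onset-anchored comparison in 7.5.2.1 is the test of the hypothesis. Name the measure (total inhalations in the week corresponds to the 7.1.2.3 mean multiplied by 7) and give its alpha and sidedness.

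In either case keep the peak-anchored comparison as descriptive and label it as before the symptom peak, which still serves the protocol's peak-based parameters.

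The cost is wording only, since 7.5.2.1 already needs the onset date. The estimated rise will probably be smaller. Events with onset within 14 days of baseline or of an earlier CE-COPD drop out. If event times are uniform over 84 days, the baseline rule removes 14/84 = 17%, or about 15 of 91 events. Full peak-anchored windows also need 14 days of data, so with a 2-day gap the added loss is only 2/84 × 91, about 2 events. The report should describe how onset was dated, because the benefit depends on it.

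### The SAP 7.1.2.3 test can show higher mean albuterol use in the 7 days before the peak, but not whether the rise came several days ahead or only in the last day or two

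*SAP*

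**What the plan says.** SAP 1.1 states the hypothesis as one about timing: "albuterol use will increase several days prior to a moderate or severe CE-COPD and can serve as a marker of COPD deterioration".

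SAP 7.1.2.3 turns it into a test. The window is fixed by "Several days will be defined as 7 days prior to the date of the CE-COPD symptom peak for this analysis". Each patient with an event contributes one number, the "mean number of puffs during the 7 days immediately preceding the date of the CE-COPD symptom peak minus mean number of puffs" for days 8 through 14 before the peak. The null is a mean difference of zero and the alternative a positive one, which "will be tested using a t-test at the 0.05 significance level". The stated purpose is "To assess if albuterol usage increases 7 days prior to a CE-COPD". The model behind the alternative adds the same shift to each of the seven days.

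SAP 7.5.2.1 makes a similar comparison anchored at symptom onset. It sets "the week immediately preceding the onset of CE-COPD symptom" against the week before that, using whole-week summaries: total, maximum and mean use, and days above thresholds.

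**The concern.** The hypothesis concerns when use rises, because a marker of deterioration needs lead time. The test collapses the seven days into one mean. The constant seven-day shift is assumed by the model but not checked by the statistic, so the alternative is true even if use on days 2–7 is unchanged and only the last day differs. A significant result could then be read as support for an early rise when the data show a late one.

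The anchor adds to this. A CE-COPD requires at least 2 consecutive days of worsening symptoms (SAP 7.5.1), so the last day or so before the peak may already lie after onset. The documents do not give the interval from onset to peak.

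**Working it through.** **Structure (no assumption needed).** Write d for the mean of days 1–7 minus the mean of days 8–14. If m of the seven days each carry k extra puffs, E[d] = mk/7, wherever in the week they fall.
- +4 puffs on the last day only: 1 × 4/7 = 0.57 puffs/day.
- +2 puffs on each of the last two days: 2 × 2/7 = 0.57.
- +0.57 puffs on all seven days: 7 × 0.57/7 = 0.57.

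The test has the same expected difference in all three cases.

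**Number of patients.** The SAP's planning figures reproduce: 360 × (1.05 + 1.14)/2 × 12/52 = 91 events. Patients with at least one event, assuming Poisson counts: 360 × (1 − exp(−91/360)) = 80. With 14 earlier study days: 80 × 70/84 = 67.

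**Assumed inputs.** The documents give no distribution of use and no effect size or power for this test. Assumed here: mean use μ = 2 or 4 inhalations/day, between-patient CV 0.75, daily variance/mean φ = 1 to 4, independent days within patient, one-sided 0.05.

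**Last-day rise by a fraction a.**
- E[d] = aμ/7
- Var(d) = φμ/7 + φμ(7 + a)/49 + a²(0.75μ)²/49
- Rejection ≈ Φ(E[d]√67/√Var(d) − 1.67)

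Doubling (a = 1):
- μ = 2, φ = 4: E[d] = 0.286, Var = 1.143 + 1.306 + 0.046 = 2.495, ratio 1.48, rejection 43%.
- μ = 4, φ = 1: E[d] = 0.571, Var = 0.571 + 0.653 + 0.184 = 1.408, ratio 3.94, rejection 99%.

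A 50% rise (a = 0.5):
- μ = 2, φ = 4: E[d] = 0.143, Var = 2.379, ratio 0.76, rejection 18%.
- μ = 4, φ = 1: E[d] = 0.286, Var = 1.229, ratio 2.11, rejection 67%.

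**Simulation of the same model** (ranges over the settings above):

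| True pattern | Days 1–7 vs 8–14 (planned) | Days 3–7 vs 8–14 |
|---|---|---|
| Doubling, last day only | 43–99% | about 4–5% |
| Doubling, last two days only | 89–100% | about 4–5% |
| 50% rise, last day only | 18–70% | about 5% (no change on days 3–7) |
| Doubling, day 3 only | same E[d] as last day only | 57–100% |

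For a true 25% rise on all seven days, the days 3–7 contrast has slightly less power: about 0.83 falls to 0.76 in the worst setting. With no rise, the planned test rejects in about 5%, so its level is sound.

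**A second use model** (fixed added puffs, gamma patient means with shape 1.5, 70 patients). With +2 puffs on the last day only, the planned test rejects in 92%, 72% and 56% at mean use 2, 4 and 6/day. With +4 puffs on that day, mean use 4/day and stronger day-to-day overdispersion (0.3 or 1.0), it rejects in 81% or 51%.

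**Other planned outputs.**
- 7.1.2.2: descriptive counts at 1, 3, 5, 7, 10, 14 and 21 days before the peak, with no contrast against an earlier week. Its mean-and-CI figure runs by study day. Its event-aligned figure covers only patients with multiple CE-COPDs.
- 7.1.2.4: days from the first threshold crossing to the peak, descriptive. The first crossing may be chance: at a steady Poisson mean of 4/day, a day at least 2 above the mean has probability 0.21, so one is expected about every 1/0.21 ≈ 5 days.
- 7.5.2.1: tested, but on whole-week summaries.
- 7.5.2.2: Kaplan–Meier plot from first heavy use to event within 7 days, with no test.
- 7.5.2.3 and 7.5.3: left to a separate group. The only example given predicts the next day.

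**The case against.** The SAP openly defines several days as the 7-day window, states its null as no increased use before an exacerbation, and gives no rule for reporting a sustained or early rise. The study is exploratory, with no primary endpoint and no power claim for this test. All of this stands, but defining a window does not make its mean a test of when use rose within it.

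A reader might infer that the plan ignores timing. It does not: 7.1.2.2 could reveal a late rise, 7.5.2.2 displays lead time, and the counts of days above 4, 8 and 12 inhalations in 7.5.2.1 carry some information on duration. Those counts can still differ significantly through one added day, and the other two outputs have no test.

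A reader might also infer that a rise in the last day or two comes too late to act on. The documents give no minimum lead time, and SAP 1.1 lists use in the 24 hours before an event among its parameters of interest.

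The size depends on assumptions. A 25% last-day rise rejects in only 12–28%. With assumed autocorrelated drift (log-SD 0.5, day-to-day correlation 0.9), a last-day doubling rejects in about 32–61% and a last-two-day doubling in 74–97%. The problem shrinks but remains.

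The days 3–7 contrast also has limits. It responds to a jump on day 3 alone (57–100%), and its two-day cut has no source in the documents. It can support a conclusion but should not decide one by itself.

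**Conclusion.** The point holds as one of interpretation. The test is valid for higher mean use in the week before the peak, and rejection supports no more than that. That it cannot place the rise within the week follows from E[d] = mk/7 and needs no assumption. How often a late-only rise would be declared significant does depend on assumptions: about 43–99% for a last-day doubling and 18–70% for a last-day 50% rise, with 67 patients, mean use 2–4/day, variance/mean 1–4 and independent days.

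A non-significant earlier-day contrast would not show that the rise was confined to the last 1–2 days. At power 0.76, a true week-long 25% rise would miss significance in 1 − 0.76 = 24% of studies.

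**What to change.** - Keep the planned test in 7.1.2.3 and word its conclusion as higher mean use in the 7 days before the peak.
- Report, aligned to the event, the within-patient mean difference from days 8–14 for each single day −1 to −7, with 95% CI.
- Add a supportive contrast that leaves out the last days, for example days 3–7 versus days 8–14, by the same t-test.
- Do the same in 7.5.2.1, anchored at symptom onset. That version bears more directly on warning, because days 3–7 before the peak may still fall after onset.
- Claim a rise several days ahead only if the earlier-day contrast is positive and the daily estimates show it is not driven by one day. If that contrast is not significant, state that an earlier rise was not demonstrated, and do not conclude that the rise was late only.

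The cost is SAP wording plus one contrast and one daily summary from inhalation records that are already timestamped. The earlier-day contrast has slightly lower power (about 0.83 to 0.76 in the worst case, for a 25% week-long rise). The planned test is unchanged.
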